11.1. Single Reference Safety Document

The respective current local product label ("Fachinformation Germany") will serve as the single reference safety document during the course of the non-interventional study, which will be used by Pfizer safety to assess any safety events reported to Pfizer Safety by the investigator during the course of this NIS. The single reference safety document should be used by the investigator for prescribing purposes and guidance.

12. PLANS FOR DISSEMINATING AND COMMUNICATING STUDY RESULTS

In the event of any prohibition or restriction imposed (eg, clinical hold) by an applicable competent authority in any area of the world, or if the investigator is aware of any new information which might influence the evaluation of the benefits and risks of a Pfizer product, Pfizer should be informed immediately.

In addition, the investigator will inform Pfizer immediately of any urgent safety measures taken by the investigator to protect the study patients against any immediate hazard, and of any serious breaches of this NI study protocol that the investigator becomes aware of.

ANNEX 1. LIST OF STAND ALONE DOCUMENTS

Number	Document reference number	Date	Title
1	Section 11	16JUN2023	B7451089_Pregnancy Reporting Process_V1_16JUN2023

ANNEX 2. ADDITIONAL INFORMATION

Not applicable.

1 INTRODUCTION

AD is a common inflammatory skin disease characterized by pruritus, eczematous lesions and its chronically relapsing course. For European countries, a prevalence of 4.4% was estimated among adults based on survey data from 2016 [1]. In Germany, approximately 13% of children and adolescents aged 0-17 years are at least temporarily affected by AD [2]. Skin manifestations typically start in childhood and can persist into adulthood [3].

Clinical signs of AD are pruritus and eczematous lesions with unpredictable periods of acute worsening (exacerbation of signs and symptoms/exacerbations) alternating with periods of relative calm after treatment. Chronic lesions are characterized by lichenification, nodulation and excoriation, and patients usually have a dry, flaky skin.

Although great strides have been made in understanding the causes, the complex pathophysiology of AD is still not completely understood. It has been established that the pathophysiology of AD includes a defective skin barrier function, allergic responses, defective antimicrobial immune defense, and a genetic predisposition. The predominant symptom of AD is pruritus, and the resulting scratching typically sets off an amplification cycle of atopic skin inflammation with an immense impact on the patients' quality of life, including physical and psychosocial effects on both patients and families [4]. The health-related impact on quality of life (QoL) correlates with disease severity and exceeds that seen in patients affected with diseases like asthma, epilepsy, and diabetes. Comorbidities include sleep deprivation from pruritus (more than 60% of AD cases), pain, anxiety, depression, suicidal ideation, obesity, food allergies, asthma, and allergic rhinitis/rhino conjunctivitis, which can be debilitating and negatively impact all areas of personal, academic, professional, and daily life for the patient and family members [4,5]. Therefore, one of the most important treatment goals should be a reduction of pruritus and that patients can report freedom from itching.

Current Standard of Care

AD management aims to improve symptoms and establish long-term disease control by avoidance of individual trigger factors, skin barrier restoration through moisturizer use, and a step-up/step-down approach aimed at reducing inflammation [6]. The choice of anti-inflammatory-therapy is largely based on AD severity/activity; mild AD can usually be controlled with topical treatments; more severe disease may require phototherapy and/or systemic immunomodulatory therapy [7]. Systemic treatment of AD is usually reserved for patients with refractory and severe disease where topical treatments of AD are not effective or have not been well tolerated. Currently only a limited number of treatments are available especially for patients with severe AD: Systemic therapy options, such as oral corticosteroids, immunomodulators such as Ciclosporin (Cyclosporin A) are associated with potentially severe adverse effects and require careful monitoring. For these reasons, the use of these agents is limited to short courses or intermittent therapy. Further, none offers a cure; therefore, the main aims of existing treatments are to reduce the occurrence of acute flares, to increase the time between

relapses, and to reduce pruritus and the resulting sleep disturbance [7-9]. Other systemic agents to treat AD are under clinical development or recently approved.

In Germany dupilumab, an injectable monoclonal antibody directed against interleukin-4 receptor alpha, was approved in 2017 and offers a novel mechanism of action for the treatment of patients (>12 years) with moderate to severe AD and children (>6 years) for the treatment of severe AD. Dupilumab inhibits signaling of interleukin (IL)-4 and IL-13, and by doing so alters type 2 helper T (Th2) cell-mediated immune responses and improves epidermal barrier abnormalities in AD. While efficacy results from clinical studies of dupilumab are compelling [10], a large proportion of subjects fail to achieve a favorable response of Investigator's Global Assessment (IGA) 0-1/Eczema Area and Severity Index (EASI-75) and continue to experience the burden of moderate to severe AD. Additionally, a slow onset of action (2 to 4 weeks), and an incomplete relief of pruritus highlights the need for faster-acting therapies that work in a larger percentage of patients, especially on pruritic symptoms. In addition, treatment with dupilumab has the risk of injection site reactions, allergic reactions, eye and eyelid inflammations and cold sores [11]. Furthermore, dupilumab is delivered via subcutaneous injection, which may not be a method of administration tolerated well by all patients.

In June 2021, the second injectable monoclonal antibody, tralokinumab received drug approval by the European Medicines Agency (EMA) for the treatment of adult patients with moderate to severe atopic dermatitis who are candidates for systemic therapy. Tralokinumab neutralizes IL-13, a cytokine which is supposed to play a key role in AD [12]. The effectiveness of tralokinumab monotherapy has been shown in the ECZTRA 1 and ECZTRA 2 trials [13]. Besides very commonly reported side effects like upper respiratory tract infections and commonly reported side effects like eye redness and itching, eye infections, and injection side reactions, tralokinumab very rarely can cause serious side effects including hypersensitivity reactions such as anaphylaxis [14].

Baricitinib, a JAK1/2 inhibitor, has been approved in 2020 as first small molecule for adult patients with moderate to severe AD who are eligible for systemic therapy. Baricitinib is taken orally as a tablet. According to the applicable summary of product characteristics of baricitinib, laboratory monitoring of lipid parameters, neutrophil count, lymphocyte count, hemoglobin, and liver transaminases should be performed while taking baricitinib. The use of baricitinib is associated with an increased risk of infections such as upper respiratory tract infections [15]

Most recently (in July 2021), upadacitinib a JAK1 inhibitor as second small molecule has been approved by the EMA for the treatment of adults and adolescents (≥12 years) with moderate to severe atopic dermatitis. Like baricitinib, upadacitinib is also taken orally as a tablet. According to the applicable Summary of Product Characteristics (SmPC) monitoring of neutrophil and lymphocyte count, hemoglobin, liver transaminases, and lipid parameters is strictly recommended. Also, upadacitinib use is associated with an increased risk of infections. The most frequent serious infections reported with upadacitinib included pneumonia and cellulitis [16].

However, there is still an unmet medical need for a conveniently administered therapy with an acceptable safety profile, for continuous and intermittent use, which is effective for moderate to severe AD and has a rapid onset of action including for the relief of pruritus.

Abrocitinib: Mechanism of Action (MoA)

Abrocitinib (PF-04965842) is an orally bioavailable small molecule being developed as an oral treatment for patients with moderate to severe AD, therefore it provides a more convenient route of administration compared with the subcutaneous injection required for dupilumab and does not have the potential risk of injection site reactions. Unlike dupilumab, abrocitinib is a small molecule and there is no anticipated immunogenicity to abrocitinib, and so it is unlikely to generate antidrug antibodies and may be used intermittently.

Abrocitinib selectively inhibits JAK-1 by blocking the adenosine triphosphate (ATP) binding site. It has a high degree of selectivity against other kinases in the human genome: 28-fold selectivity over JAK-2, >340-fold over JAK-3 and 43-fold over tyrosine kinase 2 (TYK2) as well as a good selectivity profile over the broader range of human kinases. A variety of pro-inflammatory cytokines such as IL-4, IL-5, IL-13, IL-31 and IFN-γ, have been suggested to be involved in the pathogenesis of AD. Many of these pathogenic cytokines use JAK-1 for signaling. This suggests that selective JAK-1 inhibitors that modulate the activity of these cytokines represent a compelling approach to the treatment of inflammatory skin diseases such as AD [17]. Broader inhibition of cytokines, including those important in the pathogenesis of AD, may result in an increased proportion of responders, with an acceptable safety profile.

The first Phase 3 studies, B7451012 and B7451013, that evaluated 100 and 200 mg once daily (QD) abrocitinib in participants with moderate to severe AD, which were completed in 2019, reported statistically significant improvement in efficacy endpoints in both treatment groups compared to the placebo group, with an acceptable safety profile [18,19].

Summary of Study Rationale

Currently, there is a lack of real-world data regarding the effectiveness of the new systemic treatment class of JAK inhibitors in AD in daily clinical practice in Germany. Thus, this non-interventional study was designed to gather information about non-selected patients who have been chosen to start treatment with abrocitinib in dermatological practices in Germany.

In order to gain valuable and solid insights into current and upcoming real-world treatment patterns starting with a systemic abrocitinib therapy, all subsequent therapy sequences with reasons for the respective therapy decisions will be systematically documented. Specific information on the patient's medical and clinical history, the routine clinical management including the reasons for starting treatment, management of treatment initiation, prescribed concomitant medication, its dosage, and actual use by the

treated patient will be recorded. In order to understand not only the treatment management and reasons for starting treatment with abrocitinib, but also the reasons for ending therapy with abrocitinib, all patients will be followed up for the full individual observation period of 12 months after first abrocitinib prescription after inclusion in this observational study regardless of whether they are constantly treated with abrocitinib.

Taking into account the more diverse patient population in the real-world setting, this non-interventional study will further provide additional short-and long-term real-world evidence for the effectiveness of abrocitinib in patients of medical interest and need, who may have been underrepresented in the controlled settings of clinical trials and evaluate patient-relevant endpoints including measurements of patient-reported outcomes, such as quality of life, depression, pruritus, and sleep quality.

Patient preference and satisfaction of a therapy strongly affects adherence to a prescribed medication, ultimately affecting treatment outcome and efficacy. A factor known to have an impact on patient satisfaction with a prescribed treatment is the route of administration. Here, several studies point to a preference for oral therapies. Thus, this non-interventional study will document patient's expectations and satisfaction with regards to the treatment.

Based on the collected patient characteristics (i.e., severity/duration of disease, pretreatment, comorbidities) and the heterogeneity of patient profiles encountered in a real-world setting, potential predictors of response and prognostic factors for an optimal treatment can be identified and on some of them shall be further elaborated. Hand eczema with its atopic subtype [20] already has a strong association with atopic dermatitis, [20] For instance, with atopic dermatitis and hand eczema, both, the skin barrier dysfunction associated with filaggrin mutations, is relevant [21,22]. The treatment of hand eczema is quite challenging, but anti-inflammatory treatment is important; [20,23] including JAK inhibition as an interesting new therapy approach [23,24]. The association of AD and asthma is well established [25]. It is now recognized that type 2 cytokines, like IL-4, IL-5 and IL-13, play an important pathophysiological role. [26] Successfully conducted clinical trials with dupilumab in patients with uncontrolled persistent asthma [26] and moderate-to-severe uncontrolled asthma [27] resulted in the end with a market authorization of dupilumab as add-on maintenance treatment for severe asthma with type 2 inflammation in the European Union [11]. Also allergic rhinitis and polyposis nasi, as atopic morbidities, are driven by type 2 inflammation [28], resulting in market authorization for dupilumab in the European Union for chronic rhinosinusitis with nasal polyposis [11]. Also in alopecia areata, clinical trials with JAK inhibition were conducted successfully [29,30] with baricitinib gaining market authorization in the European Union [31]. Prurigo nodularis and AD share JAK inhibition as a same treatment target (binding of IL-31 to its respective receptor [32,33] mediated through a JAK1 and JAK2 signaling pathway [34]) showing efficacy against pruritus [33]. Consequently, the impact of adequately treated AD with abrocitinib on comorbidities of interest, such as (allergic) asthma, (allergic) rhinitis, polyposis nasi, chronic hand eczema, as well as other commonly associated

comborbidities, like prurigo nodularis [32,35] and alopecia areata, [36,37] shall be assessed.

Above shown information will help to draw inferences and optimize future therapy with abrocitinib and its clinical management.

1.1 STUDY DESIGN

This prospective, single-arm, multi-center, observational non-interventional study in Germany does not interfere with the current routine practice of the treating physician. All treatment decisions, types and timing of disease monitoring, diagnostic or other medicinal procedures are at the discretion of the treating physician and patients and are not influenced or affected by the participation in this non-interventional study.

All assessments described in this protocol are performed as part of normal clinical practice or standard practice guidelines for the patient population and healthcare provider specialty in the countries where this non-interventional study is being conducted. There will be no additional diagnostic or monitoring procedures that are outside the routine clinical practice.

This is a 60-month, prospective, non-interventional, multicenter study to evaluate the effectiveness, usage and patient characteristics of real-world use of abrocitinib in patients with moderate to severe AD in a real-world setting.

Eligible patients will be followed up for 12 months from the date of enrollment. Patients who are switched from abrocitinib therapy to other therapies continue to be observed. Patient documentation is expected quarterly as per standard clinical practice.

Strength of this non-interventional study is the observation of drug prescription and follow-up visits in a daily medical care setting. Therapeutic strategies, patient selection and frequency of patient follow-up are decided by the treating physician.

The recommended schedule of activities table provides an overview of the visits that may be documented. As this is a non-interventional study none of these visits are mandatory and every visit should be scheduled according to clinical practice. According to clinical practice the HCP may schedule additional visits to those listed on the schedule of activities, in order to conduct evaluations or assessments required to protect the well-being of the patient.

Table 1. Recommended Schedule of Activities

Study period based on routine visits	Baseline (Enroll	Month	Month	Month	Month	Month
Toutine visits	ment)	1	3	6	9	12
						End of Study (EoS)
Visit Number	1	2	3	4	5	6
Informed consent	X					
Inclusion/exclusion criteria	X					
Demographic data of patient (age, sex, weight, height, ethnicity, race, smoker/non-smoker, education, occupation, alcohol consumption, insurance type)	X					
Family history of atopic diseases	X					
Clinical history (Herpes simplex, eczema herpeticum, herpes zoster)	X					
Renal and/or liver impairment	X					
Vaccination status (Herpes zoster, Covid- 19, Influenza, Varicella)	X					X
Age at initial diagnosis of AD	X					

Study period based on routine visits	Baseline	Month	Month	Month	Month	Month
routine visits	(Enroll ment)	1	3	6	9	12
						End of Study (EoS)
Previous treatments for diagnosed AD	X					
Current comorbidities	X					
If positive anamnesis at baseline exists: Improvement of asthma symptoms from baseline						X
If positive anamnesis at baseline exists: Improvement of allergic rhinitis symptoms from baseline						X
If positive anamnesis at baseline exists: Improvement of polyposis nasi symptoms from baseline						X
If positive anamnesis at baseline exists: Improvement of alopecia areata from baseline						X
If positive anamnesis at baseline exists: Improvement of prurigo nodularis from baseline						X
If positive anamnesis at baseline exists:						X

[figure not shown]
Study period based on routine visits	Baseline (Enroll	Month	Month	Month	Month	Month
routine visits	ment)	1	3	6	9	12
						End of Study (EoS)
Improvement of hand eczema from baseline						
Number of flares during the last 12 months (first visit) and since the last visit (regardless of abrocitinib treatment status*)	X	X	X	X	X	X
Number of hospitalizations due to AD during the last 12 months (first visit) and since the last visit (regardless of abrocitinib treatment status*)	X	X	X	X	X	X
Number of absent days at work/study due to AD one year before start of treatment with abrocitinib (first visit) and since the last visit (regardless of abrocitinib treatment status*)	X	X	X	X	X	X
Reasons for start of therapy with abrocitinib	X					
Reasons for discontinuation of therapy with abrocitinib		X	X	X	X	X

Study period based on	Baseline	Month	Month	Month	Month	Month
routine visits	(Enroll ment)	1	3	6	9	12
						End of Study (EoS)
Compliance with abrocitinib treatment		X	X	X	X	X
Dosage of abrocitinib used	X	X	X	X	X	X
Reasons for prescribed dosage	X	X	X	X	X	X
Type and results of laboratory check controls	X	X	X	X	X	X
Adverse events		X	X	X	X	X
Concomitant treatment AD specific (type and dosage)	X	X	X	X	X	X
Number of days with topical- treatment use (TCS, TCI) & days with emollients use three months before start of treatment with abrocitinib (first visit) and since the last visit (regardless of abrocitinib treatment status*)	X	X	X	X	X	X
Concomitant (non-AD) treatment	X					
SCORAD	X	X	X	X	X	X
EASI	X	X	X	X	X	X

Study period based on routine visits	Baseline (Enroll ment)	Month 1	Month 3	Month 6	Month 9	Month 12 End of Study (EoS)
IGA	X	X	X	X	X	X
Pruritus-NRS	X	X	X	X	X	X
PP-NRS	X	X	X	X	X	X
DLQI	X	X	X	X	X	X
POEM	X	X	X	X	X	X
MOS	X	X	X	X	X	X
PBI	X	X	X	X	X	X
EQ-5D-5L	X	X	X	X	X	X
HADS	X	X	X	X	X	X

^{*} This includes patients who discontinued treatment with abrocitinib.

Figure 1. Timelines

The planned observation period of each patient is 12 months. In this time period up to 6 visits will be documented.

Figure 2. Study Period

Table 2. Definition of time windows for study visits

In order to collect comparable study data, Visits 1 to 3 occurring ± 14 days and Visits 4 to 6 occurring ± 28 days of the scheduled visit date will be used for data analysis (interim analysis).

Visit Label	Target Day	Definition [Day window]
Enrolment	1	1
Month 1	30	16 to 44
Month 3	91	77 to 105
Month 6	182	154 to 210
Month 9	273	245 to 301
Month 12	365	337 to 393

Visits that do not meet the defined windows as displayed in the table above will also be included in the final analysis and clinical study report. Therefore, all visits will be included using the visit time slots shown below. If more than one visit appears in a 3-month window, only the visit closest to the target day will be respected.

Amended definition:

Visit designation	Target Day	Definition [Day window]
Enrolment	1	1
Month 1	30	2 to 44
Month 3	91	45 to 105
Month 6	182	106 to 210
Month 9	273	211 to 301
Month 12	365	302 to 393

However, for analysis of safety parameters, all AEs/SAEs documented within the applicable reporting period will be analyzed.

- For the lab values, if the calculated study day for the labelled baseline visit is not study Day 1, but falls within 40 days before the start of the study dosing, then that data should be used for the baseline instead of leaving baseline missing.
- For the other values, if the calculated study day for the labelled baseline visit is not study Day 1, but falls before the start of the study dosing, then that data should be used for the baseline instead of leaving baseline missing.
- If baseline is missing there will be no imputation and although the subject's data will be included in summary data it will not be included in any change from baseline analyses.

If two or more routine visits fall into the same window, keep the one closest to the Target Day. If two routine visits are equal distance from the Target Day in absolute value, the later visit should be used.

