3 FINAL ANALYSES

The final analysis will include all enrolled patients and will be carried out after all patients have reached their final visit (at Month 12). The final datasets will be extracted from the database and locked before final analysis. Any exclusions from the analysis will be agreed and documented prior to database lock.

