5.3 OTHER ANALYSIS SET

The modified Full Analysis Set (mFAS) consists of all patients who met the eligibility criteria, received at least one dose of abrocitinib and had at least one post-baseline visit. This population will be used for analysis of primary and secondary endpoints, if $\geq 10\%$ of the FAS is omitted.

The Per Protocol Set (PP) consists of all patients who met the eligibility criteria, received at least one dose of abrocitinib and completed all visits, irrespective of the time-window.

This population will be used for analysis of primary and secondary endpoints, if $\geq 10\%$ of the mFAS is omitted.

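### The amended Month 12 window still closes at day 393, so a later Visit 6 has no slot, although SAP 1.1 says all visits enter the final analysis

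*SAP*

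**What the plan says.** SAP 1.1 first gives narrow windows, "Visits 1 to 3 occurring ± 14 days and Visits 4 to 6 occurring ± 28 days of the scheduled visit date", and links them to the interim analysis. It then widens them for the final analysis: "Visits that do not meet the defined windows as displayed in the table above will also be included in the final analysis and clinical study". The means is stated next: "Therefore, all visits will be included using the visit time slots shown below". The amended slots are day 1, 2 to 44, 45 to 105, 106 to 210, 211 to 301 and 302 to 393. Where several visits share a slot, the rule is "If more than one visit appears in a 3-month window, only the visit closest to the target day will be respected". Appendix A1.1 repeats the same slots, also ending at day 393.

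On timing, SAP 1.1 says that "none of these visits are mandatory and every visit should be scheduled according to clinical practice". The follow-up length is given as a plan: "The planned observation period of each patient is 12 months. In this time period up to 6 visits will be documented". SAP 3 has the final analysis wait until all patients have reached their Month 12 visit. Neither document sets a latest date for Visit 6.

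**The concern.** The amendment is meant to stop visits being lost because they fall outside a narrow window. It does this by lowering the start of each post-baseline slot so that it meets the end of the slot before. That works for a late visit at Months 1 to 9, which falls into the next slot. Month 12 has no next slot, so a late final visit is exactly where it was before the amendment.

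At stake are the by-visit Month 12 summaries of the physician and patient scales, the last time point in the study. SAP 7 imputes nothing apart from listed exceptions, and SAP 8.2.3 excludes missing data. A patient whose only candidate visit falls after day 393 therefore leaves the Month 12 denominator although the assessment is in the database. Because physicians and patients set the visit dates, lateness could be related to disease course. The documents give no evidence on that, and no direction of bias can be stated.

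**Working it through.** **1. Reproduce the narrow table.** Target day ± 14 for Months 1 and 3, ± 28 for Months 6, 9 and 12 (SAP 1.1, Table 2):

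| Visit | Target ± tolerance | Narrow window | Amended window | Amended offset from target |
|---|---|---|---|---|
| Month 1 | 30 ± 14 | 16–44 | 2–44 | −28 / +14 |
| Month 3 | 91 ± 14 | 77–105 | 45–105 | −46 / +14 |
| Month 6 | 182 ± 28 | 154–210 | 106–210 | −76 / +28 |
| Month 9 | 273 ± 28 | 245–301 | 211–301 | −62 / +28 |
| Month 12 | 365 ± 28 | 337–393 | 302–393 | −63 / +28 |

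The narrow table reproduces exactly. All five upper limits are unchanged; only the lower limits moved.

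**2. Count the days without a slot.**
- Narrow table, days 1 to 393: 14 + 32 + 48 + 34 + 35 = 163 days unassigned.
- Amended table, days 1 to 393: 0 unassigned and no overlaps.
- Both tables: every day from 394 onward is unassigned.
- Month 12 left open at the top: 0 days unassigned up to day 450, the last day checked.

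**3. Look for another rule that would place a day-394 visit.**
- The Appendix 1 rule for additional documentation timepoints moves information to the next scheduled visit. None follows Month 12.
- The closest-visit rule chooses among visits inside a slot. It does not place a visit that has none.
- Patient questionnaires are assigned by the A1.1 windows, which also end at day 393.
- Only adverse events are exempt from the windows.

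**4. Size, under assumptions.** Neither document gives a visit-day distribution. Assume that the Visit 6 day is normal around day 365 with no mean delay. Then P(day > 393) = 1 − Φ((393.5 − 365)/SD):

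| SD (days) | z = 28.5/SD | Share after day 393 |
|---|---|---|
| 7 | 4.07 | below 0.01% |
| 14 | 2.04 | 2% |
| 21 | 1.36 | 9% |
| 28 | 1.02 | 15% |

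A mean delay of 7 days would raise the last three to 6%, 15% and 22%.

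Alternatively, assume that each appointment is booked from the previous one, with an SD of 14 days per interval. Over five intervals the SD is 14 × √5 = 31.3, z = 28.5/31.3 = 0.91, and the share is 18%.

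**5. Patients left with no Month 12 value.** Slots are filled by day, so a late Visit 5 on days 302 to 393 counts as Month 12. In a simulation of the accumulating-delay case, about 66% of patients with Visit 6 after day 393 had another visit in that slot. The share with no Month 12 value is then 18.1% × (1 − 0.66) ≈ 6%, or about 46 of 750 if every patient has all visits. With independent visit days at SD 21 the overlap is smaller: about 8.0% of patients have no value, against 8.7% with a late Visit 6.

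**The case against.** The strongest reply is that the sentence promises inclusion only through the listed slots, that the planned observation is 12 months, and that the slots cover all of it plus 28 days. On that reading day 393 is a deliberate cut-off, and a cut-off is a legitimate choice for comparable data. Part of this stands: the SAP nowhere says in words that late visits are dropped; that follows from the table. But the observation period is only planned, visits follow routine practice, and no last date for Visit 6 is set. If day 393 is a hard stop, the statement that all visits are included is wrong and still needs editing.

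Four stronger inferences are tempting and are not supported.

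- *Large losses of patients.* A reader might apply 9% to 18% to 750 and infer about 66 to 136 lost Month 12 results. That treats assumed shares as known, supposes that every enrolled patient has a Visit 6, and ignores late Visit 5 records that fill the slot.
- *Loss of the comorbidity and vaccination items.* After baseline these are scheduled only at Month 12, but SAP 6.3 analyses them as plain frequencies tied to no window. Their loss is possible but not shown.
- *A conflict with the Per Protocol Set.* SAP 5.3 admits patients who "completed all visits, irrespective of the time-window". A patient with Visit 6 on day 400 can be in that set without a Month 12 value of their own. Set membership and having a value at one time point are different things, so this is not a contradiction.
- *Damage to the main results.* The primary endpoints are at Month 3. The secondary responder rates that SAP 6.1 defines without regard to time point might still use a late visit; the SAP does not say.

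**Conclusion.** The point holds as an internal inconsistency in SAP 1.1, repeated in the A1.1 table: the amended slots do not deliver the inclusion that the text promises, and a Visit 6 on day 394 or later is left out of the by-visit Month 12 summaries. Its reach is limited to secondary summaries in a descriptive study.

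The size is unknown. Without a mean delay, the assumed scenarios put about 0% to 18% of final visits after day 393. Fewer patients would lack any Month 12 value: about 6% in the accumulating-delay case. These figures rest on normal visit timing and on complete attendance, neither of which the documents establish. The edit is worth making before database lock, so that the decision on which late visits count is not made with the data in view.

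**What to change.** In SAP 1.1 and A1.1, choose one of two routes.

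1. **Include late visits.** Assign a documented Visit 6/end-of-study visit to Month 12 when it falls after day 393, by extending the upper end of the slot. Keep the closest-to-target rule where the slot holds more than one visit. Report the distribution of actual visit days, and show Month 12 results with and without visits after day 393.
2. **Keep the limit.** State that visits after day 393 are excluded from by-visit summaries, delete the sentence that says all visits are included, and report the number excluded.

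The same edit should reconcile the labels: A1.1 heads the wide windows as interim, whereas SAP 1.1 links the narrow windows to the interim and the wide ones to the final analysis.

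The cost is a table cell and a sentence or two, plus one extra display under route 1. The downside of route 1 is that some Month 12 values come from later than 13 months, possibly well beyond if no new upper limit is set; the with-and-without display makes that visible. Route 2 leaves documented assessments unused, but says so.
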